7.3 Procedures for assessing safety

Details of adverse event and serious adverse event reporting are presented in Section 11. Any adverse events which have occurred since the previous follow-up visit **must** be reported at the next follow-up visit; there are both structured and 'free text' spaces on the case report forms (CRF) to document adverse events.

The case report forms will specifically record deaths, side-effects of CPAP therapy (particularly nasal stuffiness and obstruction, superficial nasal soreness or ulceration), cardiovascular events such as myocardial infarction or stoke, and accidents - including road accidents.

In the case of any serious adverse event (SAE) by regulatory criteria (Section 11.2), and subject to the specific adverse event recording criteria for this trial (Section 11), the recruiting centre local Principle Investigator will report the event to ORTU in keeping with regulatory reporting timelines. ORTU will manage such events in keeping with its established Standard Operating Procedures for serious adverse event assessment/management.

7.4 Other assessments

Participants will be asked to record information as stated in the flow chart (Section 7.1; Table 1). At enrolment patients will be given a folder with two Sleep Diaries with prepaid envelopes (to cover Month 1 & Month 2). At 3 month visit patients will be given a folder with 8 sleep diaries and prepaid envelopes. At the end of each month they will fill out one diary and send it back (with the exception

of the 3 and 12 months when they will be having a clinic visit). If the diaries are not received, the patient will be called as a reminder.

Questions about driving will be given to the patients by the investigator (or a research nurse) and returned directly to the ORTU. The ORTU will follow-up any incomplete or missing forms.

7.5 Loss to follow-up

Loss to follow-up will be minimised by diligent liaison of the co-ordinating centre with the Principal Investigators and the trial teams at recruiting centres with the patient, their respiratory consultant and general practitioner (GP). Every effort will be made to carry out a 12 month assessment, even in patients who have changed treatment arm, or have not attended earlier trial visits.

7.6 Trial closure

Trial closure will either be when the last patient completes follow-up or at the direction of the Trial Steering Committee (TSC) acting on the recommendation of the Independent Data Monitoring Committee (IDMC).

The IDMC will advise the TSC that the trial should be stopped if in their view there is proof beyond reasonable doubt that one of the trial treatments is clearly indicated or clearly contradicted in terms of a net difference in efficacy or safety. A difference of at least three standard errors in efficacy in an interim analysis would be needed to justify closing the study prematurely. If this criteria (Haybittle-Peto) is used the exact number of interim analyses is of little importance so no fixed schedule is proposed.

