9.3 Sample size and Power calculations

9.3.1 Subjective excessive daytime sleepiness (the Epworth Sleepiness Score)

The primary analysis will be a change in the mean Epworth Sleepiness Score (ESS) recorded monthly. In the recent NICE/HTA Technology Appraisal of CPAP for OSAHS in middle-aged patients [2], the difference in ESS for the treatment with CPAP of middle-aged patients with mild sleep apnoea was 1.07 (sd 2.4). The inclusion criterion for this trial lies in the range of "moderate" sleep apnoea by OSAHS severity, but since sleepiness is often less pronounced in older people,

power calculations are performed assuming a treatment response similar to that seen in mild disease in the middle-aged. A mean change of 1 point on the ESS is also the smallest detectable shift in the Epworth score (which is a categorical scale with one point increments), and the minimum clinically significant change since it is indicative of one symptom state shift on one domain of the score. To detect a one point change in Epworth score (sd of change 2.4), requires 244 patients randomised 1:1 (alpha=0.05, tails=2, power 90%)

In our previous randomised trials with a similar design we have found a loss to follow-up rate of 5%. Since this is a 12-month trial we have assumed the loss to follow-up rate will be 10%. Patients who cease CPAP therapy will be followed-up through the normal trial systems, with a compliance rate of zero hour being presumed. This policy is consistent with previous trials including those from which data has been used to inform these power calculations. Therefore, the sample size for this trial will be **270** patients in total randomised 1:1. A sample size table exploring other scenarios is presented in the table below.

Table 3: Sample size calculations for different mean ESS score results

Intervention Group CPAP	Control Group Best Supportive Care 90% power (alpha 0.05, 10% loss to FU)			80% pow (alpha 0.0	er)5, 10% los	ss to FU)
Change in mean ESS (SD)	0.0 (2.4)	0.1 (2.4)	0.2 (2.4)	0.0 (2.4)	0.1 (2.4)	0.2 (2.4)
1.2 (2.4)	188	224	270	140	168	202
1.1 (2.4)	224	270	334	168	202	250
1.0 (2.4)	270	334	422	202	250	314
0.9 (2.4)	334	422	550	250	314	412
0.8 (2.4)	422	550	748	314	412	560

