9.4 Interim monitoring and analyses

An Independent Data Monitoring Committee (IDMC) will monitor safety and efficacy. The IDMC will consult with the Trial Steering Committee at the start of the trial to agree its terms of reference and to set out a formal charter. The IDMC will review the trial outcomes and adverse events after each 100 patients randomised. The trial statistician will liaise with the IDMC following any Unanticipated Adverse Device Effects (UADEs) and will review the need for an extra IDMC meeting in response to such events. No interim efficacy analyses are planned by the steering committee, though the IDMC will monitor efficacy data.

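### Section 7.6 accepts safety as a ground for early closure, then makes a three-standard-error efficacy difference necessary for any early closure

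*Protocol*

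**What the plan says.** Protocol 7.6 gives two routes to trial closure: the last patient completes follow-up, or the Trial Steering Committee (TSC) directs closure on the IDMC's recommendation. Three sentences then govern early closure.

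- The first has the IDMC advise stopping if, in its view, it is proved beyond reasonable doubt that a treatment is "clearly indicated or clearly contradicted in terms of a net difference in efficacy or safety". Safety stands here as an alternative to efficacy.
- The second sets the numerical condition, and reads in full: "A difference of at least three standard errors in efficacy in an interim analysis would be needed to justify closing the study prematurely".
- The third gives the rule its Haybittle-Peto name and, because the count of looks then hardly matters, sets no timetable for them.

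Protocol 9.4 describes the monitoring: "An Independent Data Monitoring Committee (IDMC) will monitor safety and efficacy". It adds: "The IDMC will review the trial outcomes and adverse events after each 100 patients randomised". The IDMC is to consult the TSC at the start "to agree its terms of reference and to set out a formal charter". Section 9.4 gives no criterion for closing the trial, on safety or on efficacy. Section 10.5 says that the IDMC reviews safety data. Section 13.1 speaks of early answers only in terms of therapeutic advantage.

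**The concern.** The first sentence of the rule joins efficacy and safety with an 'or', so a safety difference is enough by itself. The second sentence states a necessary condition, expresses it in efficacy only, and applies it to premature closure in general. A safety signal with no matching efficacy difference meets the first sentence and fails the second.

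The protocol gives reasons to take that situation seriously. Section 2.1 raises the possibility that sleep apnoea in older people protects against later cardiac and cerebrovascular events, in which case CPAP might not benefit them. Section 11 expects that older patients may have more adverse events than the middle-aged. A cardiovascular signal need not come with any difference in sleepiness, and CPAP could improve sleepiness while a safety signal ran against it.

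What is at stake is clarity when it is needed. This is the protocol's only numerical closure criterion. Whether it covers safety should not first be argued when the IDMC has a live signal in front of it.

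**Working it through.** **The sentences side by side**

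| | First sentence of the rule (7.6) | Second sentence (7.6) |
|---|---|---|
| Ground | efficacy or safety | efficacy only |
| Standard | IDMC's view, proof beyond reasonable doubt | at least 3 standard errors (SE) |
| Logical form | sufficient to advise stopping | necessary to justify closing |
| Scope | stopping the trial | premature closure, no exception |

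For a safety-only signal the first column says advise stopping and the second says closure is not justified. Sections 9.4, 10.5 and 13.1 contain no sentence that ranks or limits the two.

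**What the literal reading would imply**

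Section 7.6 names no endpoint. The figures below take efficacy to mean ESS, which is an assumption.

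*Inputs.* Effect 1 point, SD 2.4, two-sided alpha 0.05, power 90%, 1:1 (9.3.1). Reviews after each 100 patients, so at 100 and 200 of the planned 270 (9.4, 9.3.1). As an alternative, SD 4.1, the spread of ESS improvement in the older patients of the Oxford centre (2.1). All randomised patients are assumed to have ESS data.

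*Reproducing the plan's figure.* The protocol states: "To detect a one point change in Epworth score (sd of change 2.4), requires 244 patients randomised 1:1 (alpha=0.05, tails=2, power 90"%. Per arm, n = 2 × (1.960 + 1.282)² × 2.4² / 1² ≈ 121.1, rounded up to 122, so 244 in total. This agrees. Dividing by 0.9 for 10% loss gives 271.1, or 272 with equal arms, against the stated 270. The gap is two patients and does not matter here.

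*Threshold.* Three SE corresponds to a two-sided p of 2 × (1 − Φ(3)) = 0.0027.

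*Chance of meeting it.* SE = SD × √(4/N). With a true effect of 1 point, the probability is about Φ(1/SE − 3).

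| SD | N | SE | 3 SE in ESS points | Probability, true effect 1 point | Probability, no effect |
|---|---|---|---|---|---|
| 2.4 | 100 | 0.480 | 1.44 | 0.18 | 0.0027 |
| 2.4 | 200 | 0.339 | 1.02 | 0.48 | 0.0027 |
| 4.1 | 100 | 0.820 | 2.46 | 0.04 | 0.0027 |
| 4.1 | 200 | 0.580 | 1.74 | 0.10 | 0.0027 |

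Simulation of both looks with no ESS effect gives a probability of about 0.005 that either crosses 3 SE. Adding a final test at 1.96 gives an overall two-sided error of about 0.051. So the rule does its ordinary work as an efficacy boundary.

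The primary ESS outcome uses months 3 and 4, so fewer than 100 or 200 patients would have data at the reviews. Under the 1-point effect the probabilities would then be lower. With 90 and 180 patients and SD 2.4 they are 0.15 and 0.42.

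**The case against.** The strongest reply is that 7.6 should be read as a whole. The first sentence directs the IDMC to advise stopping, rests on its judgement, lists safety as an alternative ground and attaches no SE threshold to it. The second speaks of a difference in efficacy, and the third names it Haybittle-Peto and explains why the number of looks matters little. That is a rationale for controlling false-positive efficacy findings. On this reading the 3 SE bar belongs to efficacy stops, and the literal alternative empties the words 'or safety' of meaning. The IDMC also has an explicit safety remit and a charter, which is not shown and may settle the matter.

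Much of this stands. The efficacy-only reading is probably the intended one. A reader might infer from the second sentence that the IDMC cannot justify stopping for harm unless ESS also differs by 3 SE. The documents do not support that: the preceding sentence says otherwise, and 7.6 never mentions ESS, while 9.2.1 lists two primary outcomes. Nor do they support the inference that patients would have to stay on a harmful treatment. Sections 6.5, 8, 11.3 and 13.2 let investigators, clinicians and patients interrupt, stop or change treatment individually.

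What the reply does not remove is the wording. The second sentence covers premature closure without qualification, and nothing in 7.6 or 9.4 limits it to efficacy. A charter could clarify it, but would then depart from the protocol's literal text.

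**Conclusion.** The concern holds as an internal contradiction in the stopping rule. Section 7.6 allows closure on safety and then states an efficacy-only condition for every premature closure. The label is wrong as written, and the severity is modest, because context points to the likely intent and the repair is small.

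The finding itself rests on the wording alone. The probabilities (0.0027 with no ESS effect; 0.18 and 0.48 with the planned effect and SD 2.4; 0.04 and 0.10 with SD 4.1) matter only if the literal reading is adopted, efficacy means ESS, and ESS data are complete. They are not estimates of how often a safety closure would be refused in practice. Sample size, alpha and the planned analysis are unaffected.

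**What to change.** Reconcile the two sentences in 7.6:

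1. Limit the 3 SE (Haybittle-Peto) criterion to early closure for efficacy.
2. Name the endpoint to which it applies, since 7.6 says only 'efficacy' and there are two primary outcomes. The choice is the sponsor's.
3. State that the criterion is not a precondition for closure on the safety ground already given in the preceding sentence.

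Align the IDMC charter with this text. The content of any safety criterion stays with the sponsor and the IDMC.

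The cost is one or two sentences in the protocol and the matching line in the charter. No data, sample size or alpha is given up.

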8. EARLY STOPPAGE OF TREATMENT OF PATIENTS

Patients have the right to stop treatment at any time without having to give a reason and this will not affect their future care.

a) Treatment stoppage of a participant from the trial should be under the guidance of the Principal Investigator (in liaison with the ORTU team as appropriate), details should be recorded on the relevant CRF.

b) Participants stopping treatment during this trial should continue normal trial follow up, unless consent for this follow up has been specifically withdrawn. Should a patient decide to stop follow-up, all efforts will be made to complete and report the observations as thoroughly as possible.

c) For participants moving from the area, every effort should be made for the participant to be followed up at another centre, or for follow up via GP.

d) Where patients wish to switch from Best Supportive Care to CPAP plus Best Supportive Care, this should not be encouraged and in particular not before the patient's 4 month data have been collected. For those who do switch to CPAP, follow-up in the trial will be maintained. Any proposed changes should be discussed first with the chief investigators, or the clinical trial coordinator and should be indicated on the CRF.

9. STATISTICAL CONSIDERATIONS

9.1 Method of randomisation

Participants will be allocated to the trial groups by randomisation with minimisation. This will be derived using the established randomisation systems of MRC CTU.

9.2 Outcome measures

9.2.1 Primary outcome measure

- 1. **Change in Subjective Sleepiness:** between the mean of the Epworth Sleepiness Scale (ESS) scores measured at the end of months 3 and 4 and the baseline ESS, answering the question 'does CPAP work at 3 months?'
- 2. Change in health related quality of life: Described by the EQ-5D, valued using UK population tariffs. This will be used to estimate the cost per QALY gained by providing CPAP in comparison to Best Supportive Care. The analysis will incorporate health care utilisation, including in patient and out patient hospital visits and GP visits

9.2.2 Secondary endpoints will be a change from baseline, in the following parameters at 3 and 12 months, with the exception of ESS:

- **1. Subjective sleepiness:** the mean of the ESS scores measured at months 10, 11 & 12 will be used to answer the question 'does CPAP work at 12 months?
- 2. **Objective sleepiness:** OSLER maintenance of wakefulness test
- Self-reported health status (quality of life and mood): Short Form 36 questionnaire (SF-36), and Sleep Apnoea Quality of Life Index (SAQLI; a disease specific sleep apnoea questionnaire which includes CPAP side effects), Hospital Anxiety & Depression Scale (HADS)
- 4. Functional index of activities of daily living: Townsend Disability Scale (TDS)
- 5. Frequency of nocturia: Self-reported using the patient monthly diary
- 6. **Mobility:** Timed up and go test (TUG)
- 7. Accidents: Including self-reported road, domestic and work accidents
- 8. **Cognitive function:** Mini Mental State examination, Trail making B, The Digit Symbol Substitution Test, Simple and Four-Choice Reaction Time.
- 9. **Cardiovascular risk factors:** Systolic and diastolic blood pressures, fasting glucose, fasting lipids, HbA1c.
- 10. Adverse cardiovascular events: Myocardial infarction, stroke, transient ischemic attack, new angina, new atrial fibrillation, new peripheral vascular disease

9.2.3 Tertiary endpoint will be:

1. **Treatment compliance:** Measured objectively by 'runtime' clocks built into the machines and downloaded at 3 and 12 month clinic visits.

9.3 Sample size and Power calculations

9.3.1 Subjective excessive daytime sleepiness (the Epworth Sleepiness Score)

The primary analysis will be a change in the mean Epworth Sleepiness Score (ESS) recorded monthly. In the recent NICE/HTA Technology Appraisal of CPAP for OSAHS in middle-aged patients [2], the difference in ESS for the treatment with CPAP of middle-aged patients with mild sleep apnoea was 1.07 (sd 2.4). The inclusion criterion for this trial lies in the range of "moderate" sleep apnoea by OSAHS severity, but since sleepiness is often less pronounced in older people,

power calculations are performed assuming a treatment response similar to that seen in mild disease in the middle-aged. A mean change of 1 point on the ESS is also the smallest detectable shift in the Epworth score (which is a categorical scale with one point increments), and the minimum clinically significant change since it is indicative of one symptom state shift on one domain of the score. To detect a one point change in Epworth score (sd of change 2.4), requires 244 patients randomised 1:1 (alpha=0.05, tails=2, power 90%)

In our previous randomised trials with a similar design we have found a loss to follow-up rate of 5%. Since this is a 12-month trial we have assumed the loss to follow-up rate will be 10%. Patients who cease CPAP therapy will be followed-up through the normal trial systems, with a compliance rate of zero hour being presumed. This policy is consistent with previous trials including those from which data has been used to inform these power calculations. Therefore, the sample size for this trial will be **270** patients in total randomised 1:1. A sample size table exploring other scenarios is presented in the table below.

Table 3: Sample size calculations for different mean ESS score results

Intervention Group CPAP	Control Group Best Supportive Care 90% power (alpha 0.05, 10% loss to FU)			80% pow (alpha 0.0	er)5, 10% los	ss to FU)
Change in mean ESS (SD)	0.0 (2.4)	0.1 (2.4)	0.2 (2.4)	0.0 (2.4)	0.1 (2.4)	0.2 (2.4)
1.2 (2.4)	188	224	270	140	168	202
1.1 (2.4)	224	270	334	168	202	250
1.0 (2.4)	270	334	422	202	250	314
0.9 (2.4)	334	422	550	250	314	412
0.8 (2.4)	422	550	748	314	412	560

9.3.2 Health economic analysis

The health economic analysis will involve the use of a decision model to extrapolate the trial results to a lifetime horizon. The resulting cost per QALY gained with auto-titrating CPAP with Best Supportive Care, compared to Best Supportive Care only, over a lifetime horizon will provide information to health care providers about the value of making auto-titrating CPAP available to older patients with OSAHS. The health economic analysis will be based on the difference in health related quality of life observed in the trial. A fully probabilistic analysis will be conducted such that the uncertainty in the difference in health related quality of life between CPAP and Best Supportive Care will be propagated through to the model results. This, in combination with the uncertainty in the other sources of data used to populate the decision model will allow the health economic analysis to provide an estimate of the decision uncertainty, expressed in terms of the probability that CPAP is cost-effective given a cost-effectiveness threshold of £20,000 per QALY gained.

A previous study of the effects of CPAP in patients (n=39) with diabetes and OSAHS [43] showed that CPAP may be associated with a mean improvement of 0.02 (se 0.51) in health related quality of life (which is measured on a scale between 1=full health and 0=death). The diabetic population identified by West *et al*, had not self-presented with OSAHS, which may explain why their improvement in health related quality of life was lower than the average improvement estimated for the previous analysis of CPAP middle-aged patients (mean 0.03; [2]). We can utilise the decision model from the previous cost-effectiveness analysis of CPAP in middle-aged patients [2], to extrapolate the expected improvement in health related quality of life to an improvement in QALYs. By adjusting the age of the hypothetical cohort in the model to reflect the greater age of the patient

population in this trial and adjusting the standard error of the improvement in quality of life to reflect the size of the trial, we can get an indication of the decision uncertainty that would result from this trial for a range of effect sizes. The estimates are only indicative, as the other elements of the existing decision model, such as the improvement in cardiovascular risk, may not be considered to be generalisable to an older population. The use of the effect size and standard error from the West *et al.* trial may be considered conservative as this was a very small trial in patients for whom the symptoms of OSAHS were not severe enough to cause them to seek treatment.

This trial will also provide information on any improvement in cardiovascular risk factors. The previously published trials did not provide any information as to whether use of CPAP is associated with a reduction in other health care resource utilisation. If the results of this trial indicate that the health benefits from CPAP translate to a reduction in other health care resource use, CPAP will appear more cost-effective and the decision uncertainty would be further reduced.

9.4 Interim monitoring and analyses

An Independent Data Monitoring Committee (IDMC) will monitor safety and efficacy. The IDMC will consult with the Trial Steering Committee at the start of the trial to agree its terms of reference and to set out a formal charter. The IDMC will review the trial outcomes and adverse events after each 100 patients randomised. The trial statistician will liaise with the IDMC following any Unanticipated Adverse Device Effects (UADEs) and will review the need for an extra IDMC meeting in response to such events. No interim efficacy analyses are planned by the steering committee, though the IDMC will monitor efficacy data.

9.5 Analysis plan

The Trial Management Group will develop a detailed analysis plan before treatment codes are broken.

10. DATA VERIFICATION AND SITE MONITORING

10.1 In house monitoring and Quality Control

The data will be stored in a trial database which will be developed and maintained by MRC CTU and subject to duplicate and range checks. Data stored (in line with GCP standards) in the database will be accessed from the coordinating centre at the ORTU and checked for missing or unusual values (range checks) and for consistency within participants over time. If any such problems are identified, a copy of the problematic CRF(s) will be returned to investigators for checking and confirmation or correction, as appropriate. One copy of the amended CRF(s) will be filed at the participating site and another copy will be sent to the ORTU for data entry.

